5.5 Subject Compliance Monitoring

Since the study only involves a single visit for most subjects, there will be no issues with compliance and no role for compliance monitoring.

5.6 Prior and Concomitant Therapy

Comparison imaging studies (ultrasound and MRI) completed prior, concomitantly or post-CEUS will be collected.

5.7 Packaging

- Definity comes in single use 2-mL clear glass vials.
- Lumason comes in a clear vial containing 25 mg of powder along with one pre-filled syringe with 5 mL sodium chloride 0.9% diluent.

5.8 Blinding of Study Drug (if applicable)

Does not apply.

5.9 Receiving, Storage, Dispensing and Return

5.9.1 Receipt of Drug Supplies

Upon receipt of the of the study treatment supplies at the Investigational Drug Service (IDS), an inventory must be performed and a drug receipt log filled out and signed by the person accepting the shipment. It is important that the designated study staff counts and verifies that the shipment contains all the items noted in the shipment inventory. Any damaged or unusable study drug in a given shipment (active drug or comparator) will be documented in the study files. The investigator must notify study sponsor of any damaged or unusable study treatments that were supplied to the investigator's site.

5.9.2 Storage

- Definity is stored between 2-8°C.
- Lumason is stored at 25°C; excursions permitted to 15-30°C.

5.9.3 Dispensing of Study Drug

Study drug (contrast agent) is not dispensed to the subject. It is used one-time, at the study visit and administered by study members.

5.9.4 Return or Destruction of Study Drug

At the completion of the study, there will be a final reconciliation of drug shipped, drug consumed, and drug remaining. This reconciliation will be logged on the drug reconciliation form, signed and dated. Any discrepancies noted will be investigated, resolved, and documented prior to return or destruction of unused study drug. Drug destroyed on site will be documented in the study files.

6 Study Procedures

6.1 Visit 1

After consent is signed, urinalysis and pregnancy test (if necessary) will be obtained. If the subject is cleared to proceed, IV access will be placed. Baseline B-mode US will be performed to confirm the lesions being imaged (unless it is a subject with no lesions, then a basic B-mode US will be performed). Contrast agent will be prepared by trained nursing staff. Once all study members and subject are prepared, contrast agent will be administered, and contrast enhancement of each lesion captured on a video clip. Once all lesions of interest are imaged, IV will be discontinued, and the subject discharged. Subject will be monitored throughout the study for any adverse events. See Flowchart (Appendix 1) for details.

Due to the uncommon occurrence of serious cardiopulmonary reactions, as listed in the package insert, resuscitation equipment and trained personnel will always be readily available during the study visit.

Subjects may be asked to return for an additional imaging visit the following 1-2 years for a repeat study to mirror clinical protocols for imaging in VHL.

7 Statistical Plan

7.1 Sample Size Determination

The goal of this feasibility study is to enroll a total of 15 subjects with familial syndrome at risk of kidney cancer, with at least 10 having 1 kidney lesion. This will yield up to 30 kidneys which will be assessed using CEUS, B-mode US and contrast MRI. Each of the 3 images on each kidney read by 3 readers with a Bosniak score assigned to each lesion. The primary objective is to assess agreement between the new imaging approach via CEUS with the most widely used existing technique, contrast-enhanced MRI, based on dichotomized Bosniak scores (I/II/IIF versus III/IV). A high kappa would warrant further investigation of CEUS as an alternative to MRI and other approaches. As described below in section 7.2, overall point estimates and confidence intervals will be computed for the kappa of interest based on averaging across the 3 readers. The proposed sample size will yield 95% confidence intervals with widths no greater than 0.30 over a wide range of true kappas, which should provide sufficient precision in kappa estimates to make a determination regarding feasibility of CEUS for future research.

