3.1 General Design

This study is a pilot cross-sectional study.

Study Schema:

Any patient with a familial syndrome at risk of kidney cancer (VHL, BHD, HLRCC or TSC) undergoing annual imaging screening is eligible, but we will target inclusion of at least 10 subjects who have at least 1 kidney lesion. Therefore, up to 5 subjects may have no current kidney lesions. Subject participation will be

only for the day of CEUS study. There will be no follow-up period for this study. However, if results are encouraging, a longitudinal observational study may follow, and these same subjects would be eligible for enrollment.

Abdominal imaging in patients with VHL is also used to monitor the pancreas. Although pancreatic lesions are less common than kidney lesions, cross-sectional imaging allows for monitoring of both organs. For patients with VHL, we will image the pancreas in addition the kidneys in order to establish parameters for pancreas CEUS. CEUS of the pancreas is not novel⁵¹, but its use for screening in patients at risk of pancreas lesions has not been investigated.

Following completion of imaging, all CEUS, MRI (within 4 months) and B-mode (at time of CEUS) US studies will be de-identified. Blinded radiologists will interpret images and provide an overall assessment of risk of malignancy to each kidney using the Bosniak criteria for each kidney lesion present. The Bosniak criteria places cystic lesions into one of 5 categories (I, II, IIF, III and IV) based on lesion characteristics. CEUS based diagnosis will be compared to the diagnoses on routine B-mode US and contrast-enhanced MRI.

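### Section 7.1's ceiling of 0.30 on the 95% interval width for kappa holds, as a full width, only at high agreement, and its assumptions are not stated

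*Combined protocol and SAP*

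**What the plan says.** Section 7.1 plans 15 subjects, "with at least 10 having 1 kidney lesion", and continues: "This will yield up to 30 kidneys which will be assessed using CEUS, B-mode US and contrast MRI". On scoring it says: "Each of the 3 images on each kidney read by 3 readers with a Bosniak score assigned to each lesion". The score is dichotomized as I/II/IIF against III/IV. Under section 7.2, kappa is computed per reader, averaged over the three readers, and given a 95% interval by resampling subjects.

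The precision claim is "The proposed sample size will yield 95% confidence intervals with widths no greater than 0.30 over a wide range of true kappas". The section then draws its conclusion on feasibility from that figure alone: "which should provide sufficient precision in kappa estimates to make a determination regarding feasibility of CEUS for future research". The decision it serves is also in 7.1: "A high kappa would warrant further investigation of CEUS as an alternative to MRI and other approaches".

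Neither 7.1 nor 7.2 gives a III/IV prevalence, a between-reader or within-subject correlation, numerical limits for the kappa range, a planning formula, or a statement of whether the width is full or half.

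**The concern.** This sentence is the whole sample-size justification. The width of an interval ordinarily means its full length, and a full length of 0.30 from about 30 binary ratings is tight unless agreement is high. Averaging three readers helps, but they read the same images, so they do not supply three independent samples.

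The difference affects how the result would be read. A full width of 0.30 around an estimate of 0.6 is 0.45 to 0.75. If the real interval runs from about 0.34 to 0.86, it covers both poor and excellent agreement, and the study is less able to say whether CEUS merits further work than the protocol claims.

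**Working it through.** **Inputs from the plan.** At most 30 kidneys (15 subjects, two each), 3 readers, a binary score, the mean of three reader-specific kappas, and 95% confidence (z = 1.96).

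**Inputs assumed here, because the plan gives none.** III/IV share p = 50%, 30% or 20%, equal on both modalities; correlation r between the readers' kappa estimates = 0, 0.3 or 0.5; kidneys independent.

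**Formula.** With equal marginals, the large-sample variance of one reader's kappa k is

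Var = (1 − k)/n × [(1 − k)(1 − 2k) + k(2 − k)/(2p(1 − p))].

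Averaging three readers multiplies the standard error by √((1 + 2r)/3). Full width = 2 × 1.96 × SE.

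**Worked case: k = 0.6, p = 0.3, n = 30.** Var = (0.4/30) × [0.4 × (−0.2) + 0.6 × 1.4/0.42] = 0.01333 × 1.92 = 0.0256, so SE = 0.16 and the one-reader width is 0.627. For three readers it is 0.627 × √(1/3) = 0.362 at r = 0 and 0.627 × √(2/3) = 0.512 at r = 0.5.

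**Attempt to reproduce 0.30 as a full width** (p = 50 / 30 / 20%):

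| r | kappa 0.4 | kappa 0.6 | kappa 0.8 | 0.30 met from kappa |
|---|---|---|---|---|
| 0 | 0.38 / 0.41 / 0.47 | 0.33 / 0.36 / 0.42 | 0.25 / 0.27 / 0.31 | 0.69 / 0.75 / 0.82 |
| 0.3 | 0.48 / 0.52 / 0.59 | 0.42 / 0.46 / 0.53 | 0.31 / 0.34 / 0.40 | 0.82 / 0.85 / 0.89 |
| 0.5 | 0.54 / 0.58 / 0.66 | 0.47 / 0.51 / 0.59 | 0.35 / 0.38 / 0.44 | 0.86 / 0.88 / 0.91 |

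The intervals at kappa 0.6 are 0.43 to 0.77 for p = 50% and r = 0, and 0.34 to 0.86 for p = 30% and r = 0.5. Correlation of kidneys within a subject, which 7.2 anticipates, widens them further: with an assumed intraclass correlation of 0.5, independent readers and p = 50%, the width at kappa 0.6 rises from 0.331 to 0.331 × √1.5 = 0.405.

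**As a half-width.** The largest value over all kappas is 0.21 / 0.21 / 0.24 at r = 0 and 0.29 / 0.30 / 0.335 at r = 0.5. On this reading the statement roughly reproduces.

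**Dropping equal marginals.** A search over all 2×2 tables at fixed kappa, with the general delta-method variance and independent readers, gives smallest widths of 0.28, 0.296, 0.295 and 0.278 at kappa 0.4, 0.5, 0.6 and 0.7. These need all disagreement to run one way with a III/IV share near 50%, for example 40% on one modality and 61% on the other at kappa 0.6. At r = 0.1 they become 0.307, 0.324, 0.323 and 0.304.

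**At the plan's stated minimum.** Ten subjects with one lesion each give 10 lesion-bearing kidneys out of 30. If lesion-free kidneys count as not III/IV (the plan does not say), p cannot exceed 33%. With both marginals capped there and independent readers, the smallest width over any table is 0.37 at kappa 0.4, 0.35 at 0.6 and 0.315 at 0.7. The 0.30 limit needs kappa of about 0.73.

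**Small-sample check.** A simulation of the planned subject bootstrap (15 subjects, two kidneys, three independent readers) gave mean full widths at kappa 0.6 of 0.318, 0.355 and 0.429 for p = 50, 30 and 20%. The share of simulated trials at or below 0.30 was 42%, 22% and 5%.

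**The case against.** The plan fixes none of the quantities needed to contradict its figure, so every width above 0.30 rests on values chosen here. What the text alone proves is an unstated basis. That is right as far as it goes, but the shares cover 20% to 50%, 50% is the most favourable value under equal marginals, and the claim still fails at kappa 0.6 there with fully independent readers.

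The half-width reading reproduces, comfortably so with independent readers. This stands, and it may be what was meant. The text does not say so, and a total length of 0.30 and a margin of ±0.30 support very different conclusions.

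The decision concerns a high kappa, where the full-width claim is partly true: at kappa 0.8 with independent readers it is met for shares of 50% and 30%. It is not met there at 20%, or at any of the three shares with reader correlation 0.5. Agreement from about 0.7 upward is also hard to describe as a wide range.

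The one-directional pattern is a genuine counterexample, but it disappears at a reader correlation of 0.1.

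The unit may be the lesion. Section 3.1 has readers "provide an overall assessment of risk of malignancy to each kidney using the Bosniak criteria for each kidney lesion present" and says "we will target inclusion of at least 10 subjects who have at least 1 kidney lesion", so more than 30 lesions are possible and the 33% cap describes only the minimum. With 60 independent lesions and independent readers, the width at kappa 0.6 is 0.234 / 0.256 / 0.295. But no lesion count is planned, 7.1 counts kidneys, clustering of lesions would widen the interval, and the guaranteed minimum of 10 lesions gives 0.57 / 0.63 / 0.72.

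Finally, this is a pilot study with no kappa success threshold. That limits the consequence and is why no larger sample is requested.

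**Conclusion.** The concern holds. As a full width, 0.30 is reached only at high agreement: from kappa of about 0.69 to 0.82 with independent readers, and from about 0.86 to 0.91 at reader correlation 0.5, for III/IV shares of 50% to 20%. These figures assume 30 independent kidneys and equal marginals; thirty is the plan's ceiling, and fewer or positively correlated kidneys would widen the intervals. The exceptions are a half-width reading, one-directional disagreement near 50% prevalence with fully independent readers, and an unplanned larger number of lesions as the unit. None is stated in the plan. The fault lies in the justification, not in the analysis: the planned bootstrap interval will still be reported. It should be fixed, but it does not threaten the conduct of the study.

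**What to change.** Rewrite the precision statement in section 7.1 so that it:

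- says whether full width or half-width is meant;
- names the unit of analysis, kidney or lesion, and how lesion-free kidneys and kidneys with several lesions enter the kappa;
- gives the sponsor's own assumed III/IV prevalence, between-reader and within-subject correlation, kappa range and calculation method;
- replaces the single ceiling with the widths those assumptions yield.

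The values must be the sponsor's. As a guide to scale, the scenarios above with 30 kidneys and equal marginals give full widths of 0.25 to 0.47 with uncorrelated readers and 0.35 to 0.66 at correlation 0.5, for kappas from 0.8 down to 0.4. If a half-width was intended, inserting that word and the assumptions is enough. In either case, the claim of adequate precision should be qualified to match the restated width.

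The cost is one sentence or short paragraph. Sample size, endpoint and analysis stay as they are; the only downside is a less favourable stated precision.

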7.2 Statistical Methods

Kappas will be calculated separately for each reader for CEUS versus B-mode US, CEUS versus contrast MRI, and B-mode US versus contrast MRI, using the dichotomized Bosniak score. Confidence intervals for kappas will be computed by bootstrapping subjects, accounting for potential correlations of kidneys within subjects. Differences in agreement between readers will be based on comparing reader specific kappas, with statistical significance of these differences tested via bootstrapping. An overall kappa will be computed for each paired imaging comparison by averaging kappas across readers, with a 95% interval calculated via bootstrapping. Differences in overall kappas for the 3 paired imaging comparisons will be assessed using a bootstrap test. The above analyses will also be done separately for kidneys with lesions and without lesions, to evaluate whether agreement varies in these two important subgroups. Agreement between readers will be determined separately for each imaging modality by computing kappas for all pairs of readers, along with bootstrap confidence intervals. An overall assessment of reader agreement for each of the 3 modalities will be calculated by averaging the pairwise kappas. Finally, weighted kappa analyses will be done using the raw 5-point Bosniak scores, similar to those for the dichotomized Bosniak scores.

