9	DATA HANDLING AND RECORD KEEPING.....	14
9.1	CONFIDENTIALITY.....	14
9.2	SOURCE DOCUMENTS	15
9.3	CASE REPORT FORMS (AS APPLICABLE).....	15
9.4	RECORDS RETENTION.....	15
10	STUDY MONITORING, AUDITING, AND INSPECTING	15
10.1	STUDY MONITORING PLAN.....	15
10.2	AUDITING AND INSPECTING	15
11	ETHICAL CONSIDERATIONS	16
12	STUDY FINANCES	16
12.1	FUNDING SOURCE.....	16
12.2	CONFLICT OF INTEREST	16
12.3	SUBJECT STIPENDS OR PAYMENTS	16
13	PUBLICATION PLAN	16
14	REFERENCES	16
15	APPENDICES	20

List of Abbreviations

VHL – von Hippel-Lindau
CEUS – Contrast-enhanced ultrasound
US – ultrasound
CT – computed tomography
MRI – magnetic resonance imaging
RCC – renal cell carcinoma
NSF – nephrogenic sclerosing fibrosis
FDA – Food and Drug Administration
CPS – cadence pulse sequencing
BHD – Birt-Hogg-Dube syndrome
HLRCC – Hereditary Leiomyomatosis and Renal Cell Carcinoma
TSC – Tuberous Sclerosis Complex (TSC).

Study Summary

Title	Cross-Sectional Study of Contrast-Enhanced Ultrasound with Lumason/Definity as a Screening Tool for Kidney Cancer in Patients with Von Hippel-Lindau
Short Title	CEUS VHL
Protocol Number	LCCC1824
Phase	NA
Methodology	Cross-sectional Observational Study
Study Duration	12 months
Study Center(s)	UNC-CH
Objectives	To determine accuracy of CEUS for detection of malignancy kidney lesions in patients with Von-Hippel Lindau
Number of Subjects	15
Diagnosis and Main Inclusion Criteria	Von-Hippel Lindau, Birt-Hogg-Dube syndrome, Hereditary Leiomyomatosis, Renal Cell Carcinoma, or Tuberous Sclerosis Complex Key inclusion criteria: Undergoing kidney surveillance with MRI
Study Product, Dose, Route, Regimen	Microbubble contrast agent (IV infusion): 1. Perflutren Lipid Microspheres (Definity) 2. Sulfur hexafluoride Lipid (Lumason)
Duration of administration	15 minutes
Reference therapy	Contrast-enhanced MRI
Statistical Methodology	Kappa statistics

1 Introduction

This document is a protocol for a human research study. This study is to be conducted according to US and international standards of Good Clinical Practice (FDA Title 21 part 312 and International Conference on Harmonization guidelines), applicable government regulations and Institutional research policies and procedures.

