1.5 Dose Rationale and Risk/Benefits

Dosages for both Definity and Lumason are based on package inserts, expert opinion from radiologists who routinely use CEUS for kidney imaging, and our previous experience from clinical trials (IRB 12-2314, 15-1866, 17-1130). Because the kidney is a very vascular organ, use of 0.2mL Definity has been adequate for visualization of lesion enhancement. Our experience has been with both bolus doses of 0.2mL and infusion at set rates based on BMI. The infusion rate can be increased or decreased if visualization is not adequate. Use of either small boluses or infusion allows for multiple injections for patients with multiple lesions. Patients with greater abdominal girth and multiple lesions may require a 2nd dose as their bolus doses or rate of infusion will be higher. In the case of a 2nd dose, a 30-minute interval between injections will be instituted. All microbubble contrast agents are injected intravenously.

The greatest risk is of an unknown hypersensitivity reaction to the microbubbles as many patients will not have previous exposure to these contrast agents. However, the rate of true allergic reactions is low and similar to that for gadolinium-based contrast agents. Other risks are transient and resolve when the contrast agent is cleared. Overall the risk is minimal. Benefits include improved visualization of kidney lesions compared to non-contrasted ultrasound and the potential reduction of total lifetime load of gadolinium and improvement in cost-effectiveness.

2 Study Objectives

Primary Objective

To assess the agreement between CEUS and routine B-mode US for detecting indeterminate features of kidney lesions as graded on a Bosniak scale in patients with VHL under abdominal imaging surveillance.

Secondary Objective

[figure not shown]
To assess the agreement between CEUS and contrast-enhanced MRI for detecting indeterminate features of kidney lesions as graded on a Bosniak scale in patients with VHL under abdominal imaging surveillance.

3 Study Design

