3.2 Primary Study Endpoints

The primary study endpoint will be agreement of qualitative radiologist review of CEUS images with routine B-mode US.

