3.3 Secondary Study Endpoints

The secondary study endpoint will be agreement of qualitative radiologist review of CEUS images with contrast-enhanced MRI.

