4.2.6 Female patient who is pregnant or lactating

4.2.7 Obesity that limits obtainment of acceptable images

4.3 Subject Recruitment and Screening

Subjects will be recruited from the UNC von Hippel-Lindau Clinical Care Center, under the directorship of [name], NP and [name]. UNC currently has 20-25 patients who undergo annual screening. No specific handouts will be used as the target population is very specific. Principal investigator and sub-investigators will approach patients that meet inclusion and exclusion criteria to determine interest in participation. There are no laboratory tests required. Prior imaging to determine if any lesions are present (as we are targeting at least 10 subjects who have at least one lesion) will be required.

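### Section 7.2 plans only kappas, which do not show whether CEUS-MRI disagreements are missed III/IV kidneys or overcalls and which break down for kidneys without lesions; the primary comparator also differs between sections.

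*Combined protocol and SAP*

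**What the plan says.** The Study Summary gives the objective as "To determine accuracy of CEUS for detection of malignancy kidney lesions in patients with Von-Hippel Lindau", names contrast-enhanced MRI as the reference and lists kappa as the method. The body of the protocol speaks of agreement. The primary objective in Section 2 is "To assess the agreement between CEUS and routine B-mode US for detecting indeterminate features of kidney lesions", and Section 3.2 follows it: "The primary study endpoint will be agreement of qualitative radiologist review of CEUS images with routine B-mode US". Section 3.3 puts MRI second: "The secondary study endpoint will be agreement of qualitative radiologist review of CEUS images with contrast-enhanced MRI". Section 7.1 instead makes agreement with contrast-enhanced MRI the primary objective, on the dichotomy I/II/IIF versus III/IV, and says that a high kappa would justify further study of CEUS as an alternative to MRI.

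The analysis in Section 7.2 begins: "Kappas will be calculated separately for each reader for CEUS versus B-mode US, CEUS versus contrast MRI, and B-mode US versus contrast MRI". It then averages kappas over the three readers, tests differences between kappas, repeats the analyses separately for kidneys with and without lesions to see whether agreement differs, computes kappas between readers, and ends with weighted kappas on the five-category scale. No cross-table, sensitivity, specificity or positive and negative agreement is planned.

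On scoring, Section 3.1 has readers "provide an overall assessment of risk of malignancy to each kidney using the Bosniak criteria for each kidney lesion present" and adds: "The Bosniak criteria places cystic lesions into one of 5 categories (I, II, IIF, III and IV) based on lesion characteristics". None of the five categories means that no lesion was seen. Up to 5 of the 15 subjects may have no lesion, and Section 7.3 analyses all subjects.

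**The concern.** In surveillance for kidney cancer, a kidney that MRI rates III/IV and CEUS does not is a different finding from the reverse. Kappa is unchanged when the two modalities are exchanged, so the same value can come from either pattern. The decision described in Section 7.1 concerns CEUS in the place of MRI, and the planned output would not say which kind of disagreement lies behind the kappa.

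Three related gaps add to this. The lesion-free subgroup has few or no III/IV calls, and kappa fails there. The rules for a kidney with no lesion seen are not written out, nor is the source that decides which kidneys count as lesion-free. A reader also cannot tell which of two comparisons is primary, or what would answer the accuracy objective.

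**Working it through.** The plan gives no figure on this point. Section 7.1 states a width for the kappa interval, but nothing here depends on it. The documents supply up to 30 kidneys, three readers, the dichotomy, and up to 5 lesion-free subjects (10 kidneys). All cell counts below are assumed, for one reader.

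Write a table as (both III/IV; CEUS only; MRI only; neither) = (a; b; c; d), with n = a+b+c+d. Then po = (a+d)/n, pe = [(a+b)(a+c) + (c+d)(b+d)]/n², and kappa = (po − pe)/(1 − pe). Positive percent agreement with MRI is a/(a+c); negative is d/(b+d).

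**Direction of disagreement**

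- Four misses, (6;0;4;20): po = 26/30 = 0.867, pe = (6×10 + 24×20)/900 = 0.600, kappa = 0.267/0.400 = 0.667. Positive agreement 6/10, negative 20/20.
- Four overcalls, (6;4;0;20): po and pe are the same, so kappa = 0.667. Positive agreement 6/6, negative 20/24.
- These tables are transposes, so the number of MRI III/IV kidneys also changes, from 10 to 6. With 10 held fixed, four overcalls give (10;4;0;16): pe = (14×10 + 16×20)/900 = 0.511, kappa = 0.356/0.489 = 0.727, against 0.667 for four misses.

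**Kidneys without lesions**

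If a reader makes no III/IV call on MRI in this subgroup, a = c = 0. Then po = d/n and pe = (b×0 + d×n)/n² = d/n, so po = pe. The same holds with the modalities exchanged. For 10 kidneys:

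- (0;0;0;10), 10/10 agree: po = pe = 1, kappa = 0/0.
- (0;1;0;9), 9/10 agree: po = pe = 0.90, kappa = 0.

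**Leaving out kidneys with no lesion seen**

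- (7;1;2;20): po = 0.900, pe = (8×9 + 22×21)/900 = 0.593, kappa = 0.754.
- Drop one miss that CEUS did not see, (7;1;1;20): po = 27/29 = 0.931, pe = (8×8 + 21×21)/841 = 0.600, kappa = 0.827.
- Drop 14 concordant negatives as well, (7;1;1;6): po = 13/15 = 0.867, pe = (8×8 + 7×7)/225 = 0.502, kappa = 0.732.

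**Weighted kappa**

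One assumed table, as CEUS/MRI cells: none/none 10, none/I 1, I/I 4, I/II 1, II/II 3, II/IIF 1, IIF/IIF 2, IIF/III 1, none/III 1, III/III 2, III/IV 1, IV/IV 3. With linear weights, weighted kappa = 1 − (observed sum of category distances)/(sum expected from the margins).

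- A no-lesion level below I, all 30 kidneys: 1 − 9/59.4 = 0.848.
- The 20 kidneys with a lesion on at least one modality: 1 − 9/35.6 = 0.747.
- The 18 kidneys scored on both: 1 − 4/29.78 = 0.866.

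**Precision of the added measure**

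The exact 95% interval for 6/10 runs from the 0.025 quantile of Beta(6, 5) to the 0.975 quantile of Beta(7, 4): 0.26 to 0.88, before any allowance for two kidneys per subject.

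**The case against.** Kappa is a conventional choice for agreement, and agreement is what Sections 2, 3.2, 3.3 and 7.1 state. The study is a 15-subject pilot that decides only on further research, and the 2x2 counts underlie every kappa and could be reported without a plan change. All of this stands. It supports keeping the overall kappas and labelling the additions descriptive. It does not remove the gap, because nothing in the plan commits to showing the counts.

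Four stronger readings are tempting and should be resisted.

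- A reader might infer that the study fails its real objective, accuracy. The word rests on one line of the Study Summary, which itself names kappa as the method. Percent agreement with MRI would not be accuracy for malignancy either, since no histology or follow-up standard is planned.
- A reader might infer that misses and overcalls always give the same kappa. With the number of MRI III/IV kidneys fixed they do not (0.667 and 0.727). The value still does not identify the direction.
- A reader might infer that excluding unseen kidneys inflates kappa. It can move either way, as the 0.827 and 0.732 show.
- A reader might infer that lesion-free kidneys are left out, or that their place on the dichotomy is unknown. The kidney-level read in Section 3.1, the subgroup in Section 7.2 and the population in Section 7.3 all imply that they stay in and count as not III/IV. Section 4.3 offers one possible source of lesion status ("Prior imaging to determine if any lesions are present"), and Section 6.1 has lesions confirmed on B-mode. What is missing is the statement of the rule and of the source used for the subgroup.

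**Conclusion.** The point holds as a worthwhile change to a pilot plan; it is no fatal flaw. Three parts are firm on the text: the planned kappas do not reveal the direction of CEUS-MRI disagreement, Sections 2 and 3.2 contradict Section 7.1 on the primary comparator, and the Study Summary's accuracy objective has no matching analysis.

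The failure of the lesion-free subgroup kappa is algebraic, but conditional: it applies to any reader with no III/IV call on one of the two modalities in that subgroup. It does not follow that the kappa is 0 or undefined whatever the data. Where the condition holds, 9/10 agreement yields kappa 0, which would be misread as poor agreement, and the comparison that Section 7.2 intends cannot be made.

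The scoring and accuracy parts are mainly clarification. The sizes shown rest on assumed counts; the documents give no expected number of III/IV kidneys.

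**What to change.** Keep the planned overall kappas and make these changes in Section 7.2:

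- Add, as descriptive results from the same reads, per-reader and reader-averaged 2x2 counts with positive and negative percent agreement of CEUS, and of B-mode US, against contrast MRI on the III/IV dichotomy. Note that each reader's own MRI read is the reference and that intervals will be wide.
- For kidneys without lesions, report counts and raw agreement instead of kappa. Fix lesion status by one stated source that is the same for all readers and modality pairs.
- State that a kidney is scored by its highest category, and that a kidney with no lesion seen on a modality counts as not III/IV and stays in the analysis.
- State the weights of the five-category weighted kappa. Report it on kidneys scored on both modalities, with the number excluded, and give a version with a no-lesion level as a sensitivity analysis.

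Then reconcile the Study Summary and Sections 2, 3.2, 3.3 and 7.1 on the objective and primary comparator, and describe any accuracy statement as relative to contrast MRI.

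The cost is a few tables from data already planned, some written rules and one wording reconciliation, with no added subjects, scans or reads. Two limits should be stated. Because lesions are known from prior imaging and confirmed on B-mode, the added measures reflect characterisation more than unaided detection. Scoring by kidney can also count III/IV calls on two different lesions as agreement, so such kidneys should be listed.

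### Section 7.2 plans kappas in kidneys without lesions, where the score has no defined value and kappa under negative coding is 0 or 0/0 whenever either modality makes no III/IV call

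*Combined protocol and SAP*

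**What the plan says.** - **Planned analysis (7.2).** The modality-pair kappas by reader, their bootstrap intervals and tests, and the three-reader averages are to be repeated by lesion status: "The above analyses will also be done separately for kidneys with lesions and without lesions". The purpose is to see whether agreement differs between the two subgroups. Weighted kappas on the five-point score are to follow similar lines.
- **Scoring (7.1).** "Each of the 3 images on each kidney read by 3 readers with a Bosniak score assigned to each lesion". The dichotomy is I/II/IIF versus III/IV.
- **Scale and kidney-level reading (3.1).** The categories run from I to IV, with none for absence of a lesion. Readers are to "provide an overall assessment of risk of malignancy to each kidney using the Bosniak criteria for each kidney lesion present".
- **Size of the subgroup (3.1).** "Therefore, up to 5 subjects may have no current kidney lesions". Section 7.1 expects up to 30 kidneys, and 7.3 uses all subjects.
- **Sources of lesion status.** Section 4.3 requires "Prior imaging to determine if any lesions are present", for recruitment. Section 6.1 adds: "Baseline B-mode US will be performed to confirm the lesions being imaged". Neither is linked to the kidney-level subgroups in 7.2. In 3.1 the B-mode study to be compared is the one done at the time of CEUS.

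**The concern.** Three items needed for the lesion-free subgroup are not stated: the code for a read with no lesion, the rule that turns several lesion scores into one kidney score, and the source that decides which kidneys are lesion-free.

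The code matters most. Under negative coding the subgroup is expected to hold few or no III/IV calls, and kappa breaks down there. Two modalities that agree perfectly that nothing suspicious is present give no kappa at all. One stray III/IV call gives a kappa of 0, which reads as no agreement beyond chance. A prespecified subgroup could then return no estimate or a misleading zero, and the stated comparison between subgroups could not be made on kappa. Settling these items after the reads are seen would also leave room for result-driven choices in a very small sample.

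**Working it through.** The plan gives no figure for this subgroup. The interval width of 0.30 in 7.1 concerns the overall kappa and is not at issue here.

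**Inputs.** From 3.1 and 7.1: 15 subjects, at least 10 with a lesion, up to 30 kidneys. With two kidneys each, lesion-free kidneys number at most 5 × 2 + 10 × 1 = 20 (ten unaffected second kidneys) and at least 0. Call rates are not in the documents, so those below are assumptions.

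**Algebra.** Write a table as (both III/IV, first modality only, second only, neither), with kappa = (po − pe)/(1 − pe). Suppose one modality makes no III/IV call and the other makes a share b. Then po = 1 − b and pe = 1 − b. Kappa is 0/b = 0 if b > 0, and 0/0 if b = 0. Linear-weighted kappa behaves the same way when one modality is constant.

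**Ten kidneys.**

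| Table | Raw agreement | pe | Kappa |
|---|---|---|---|
| (0,0,0,10) | 100% | 1.00 | 0/0 |
| (1,0,0,9) | 100% | 0.82 | 1.00 |
| (0,1,0,9) | 90% | 0.90 | 0 |
| (1,1,0,8) | 90% | 0.74 | 0.16/0.26 = 0.62 |

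At the same raw agreement, one kidney moves kappa across most of its range.

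**Bootstrap for (0,1,0,9).** Assume 5 subjects with 2 kidneys each. The subject with the discordant kidney is absent from a resample with probability (4/5)^5 = 0.328, and kappa is then undefined. In every other resample one modality is still constant, so kappa is exactly 0. The interval is [0,0], with about 33% of resamples undefined.

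**Lesion status taken from a compared read.** If that read finds no lesion and absence is coded negative, it is constant in the subgroup. Every pair that includes it gives 0 or 0/0. The remaining pair is not forced: if B-mode is the stratifying read, CEUS versus MRI can still give other values.

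**Lesion status taken from an outside source.** Let p be the independent false III/IV rate per modality, s the share of kidneys with a III/IV lesion seen by both modalities, and n the number of kidneys.

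- A = [(1 − s)(1 − p)]^n: one given modality is all negative.
- B = [(1 − s)(1 − p)²]^n: both are all negative, so kappa is 0/0.
- P(0 or 0/0) = 2A − B.

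Example: p = 0.02, s = 0.05, n = 10 gives A = 0.931^10 = 0.489, B = 0.912^10 = 0.400, and 2A − B = 0.579.

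| n | s | p = 2% | p = 5% | p = 10% |
|---|---|---|---|---|
| 10 | 0 | 97% | 84% | 58% |
| 10 | 5% | 58% | 50% | 34% |
| 20 | 0 | 89% | 59% | 23% |
| 20 | 5% | 32% | 21% | 8% |

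These are for one reader. One undefined reader leaves the three-reader average undefined as well.

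**All-kidney kappa.** Ten lesion kidneys (4,1,1,4) give (0.80 − 0.50)/0.50 = 0.60. Adding 20 concordant lesion-free kidneys gives (4,1,1,24): po = 28/30 = 0.933, pe = 650/900 = 0.722, kappa = 0.76. The mix of kidneys therefore shifts this kappa.

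**The case against.** The strongest reply is that the gap is small and the intent clear. Sections 7.1 and 7.3 bring all kidneys and subjects into the analysis, so lesion-free kidneys presumably enter as negative. Section 3.1 asks for a judgement on each kidney. Prior imaging is required before enrolment, so lesion status is known in advance. The study is a 15-subject pilot, the subgroup is not an endpoint, and a 0/0 would be noticed and reported as not estimable.

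Much of this stands. Negative coding is the likely intent, and a reader should not infer that the subgroup will simply have no data. Nor should a reader infer that the plan has no way of knowing lesion status; what is missing is the link to the kidney-level analysis. But negative coding is the very reading that produces 0 or 0/0, and an exact 0 with interval [0,0], unlike 0/0, looks like a result.

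Two stronger readings are tempting, and the documents do not support them:

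- **That every kappa in the subgroup must fail.** This is certain only for pairs that include a read which itself defines lesion status. The documents do not say that any compared read will do so. The baseline B-mode in 6.1 is a visit-day step, whereas the compared reads are blinded reads of de-identified images; shared images would not make them the same read.
- **That the all-kidney kappa cannot be interpreted.** It does shift with the share of lesion-free kidneys, but 7.2 already plans the kappa in kidneys with lesions, which isolates agreement on lesion grade. What remains is to print the count.

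**Conclusion.** The point holds and should be addressed. Followed as written under the natural coding, 7.2 gives 0 or 0/0 in kidneys without lesions whenever at least one modality makes no III/IV call. That result is exact and needs no assumption about call rates. How often it would happen does depend on assumed, independent rates: from 97% down to 34% for 10 kidneys, and from 89% down to 8% for 20, over the range shown. The bootstrap shares rest on 5 subjects with 2 kidneys each and do not carry over to a subgroup that includes unaffected second kidneys. The comparison of kappas between the two subgroups is unreliable. The kappa already planned in kidneys with lesions is not undermined.

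**What to change.** In 7.2:

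1. In kidneys without lesions, replace kappa, weighted kappa and their bootstrap tests with raw percent agreement per modality pair and the III/IV-call proportion per modality and reader. Give subject-clustered 95% intervals, or exact intervals when the count is 0 or n, because a bootstrap then has zero width.
2. Report the same raw percent agreement in kidneys with lesions, beside the kappa already planned there. Base the comparison between subgroups on it, noting that raw agreement also depends on the share of III/IV calls.
3. Define lesion status per kidney from one source that is fixed before the blinded reads and is not a compared read. The clinical report of the prior imaging in 4.3 would serve, or an earlier report where that scan is the study MRI.
4. Code a read with no lesion as negative for the dichotomised score. Reduce several lesions to one kidney score by one stated rule, for example the highest score per reader and modality.
5. Keep the all-kidney kappa and print the number of lesion-free kidneys beside it.

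The cost is SAP wording and a little more reporting, with no new images or reads. There would be no single kappa contrast between subgroups, and the estimates stay imprecise. Ignoring clustering, the lower exact 95% limit for n out of n is 0.025^(1/n), so 10/10 gives 69–100% and 20/20 gives 83–100%.
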